4.7.2.4 Time to Disease Flare

Time to (first) flare is defined as:

$$\text{date of first flare} - \text{date of first dose} + 1$$

For the purpose of the analysis, only flares occurring on or after Day 1 in patients who have previously achieved disease control will be analyzed. Flares occurring during the screening corticosteroid taper period will not be considered. Note that patients may not necessarily be in a state of disease control at Day 1; however, date of first dose (Day 1) will be used as the primary time origin as it is more reliable and less subjective than the date of disease control, which is determined by the investigator.

Time to disease flare during steroid taper and time to disease flare during CS withdrawal will be analyzed separately for the mITT population.

Data will be censored as follows:

- Patients withdrawing early from the study who do not experience a flare prior to withdrawal will be censored at the time of study withdrawal.
- Patients completing the 52-week treatment period who do not experience a flare will be censored at the date of study completion.

Time to first flare will be summarized using Kaplan-Meier curves along with the median, 95% confidence interval for the median, 25th and 75th percentiles for each treatment group if available. The log-log transformation will be used to compute the 95% confidence intervals.

A stratified log-rank test will be used to test the time to first flare between the RTX and MMF treatment arms over the 52-week treatment period, adjusting for the stratification factors used at randomization.

Rituximab—F. Hoffmann-La Roche Ltd
23/Statistical Analysis Plan WA29330

The time to first flare will be converted to weeks for the presentation of Kaplan-Meier curves and all associated statistics. The Proc Lifetest procedure in SAS will be used to generate the Kaplan-Meier curves and hypothesis testing.

Sensitivity Analyses

The analysis of time to disease flare will be repeated using disease control as the origin, defined as follows:

$$\text{time to disease flare} = \text{date of first flare} - \text{date of disease control} + 1$$

This sensitivity analysis aims to evaluate the onset of flares after the disease is adequately controlled. Patients withdrawing from the study who fail to achieve disease control prior to withdrawal will be excluded from the analysis.

All other methods including censoring methods will remain the same.

4.7.2.5 Dermatology Life Quality Index

The DLQI is a validated patient-reported outcome consisting of 10 questions assessing the impact of dermatologic diseases on patients' lives over the past seven days (Finlay and Khan, 1994). The DLQI questions are categorized into the following domains:

- Symptoms and feelings
- Daily activities
- Leisure
- Work and school
- Personal relationships
- Treatment

Responses to questions are ordinal in nature ranging from “Not at all” to “Very much”. The DLQI will be completed and calculated as per the DLQI instructions for use and scoring manual (Appendix 6). The DLQI has a minimum score of 0 and a maximum score of 30, with higher scores indicating greater impairment on quality of life. A change in DLQI score of at least 4 points is considered clinically important (Basra et al, 2015).

Change from baseline to Week 52 in DLQI will be analyzed using a maximum likelihood-based repeated measures model. The analysis will adjust for treatment arm, region, duration of illness, baseline DLQI score, visit, and an interaction term for visit × baseline DLQI score. An appropriate variance structure will be used to model the within-patient errors. The Kenward-Roger approximation will be used to estimate denominator degrees of freedom. Rescue data will be set to missing, otherwise data will be used in the analysis as observed. Missing DLQI scores will be handled within the framework of the repeated measures model, this includes data missing due to withdrawal or rescue.

Rituximab—F. Hoffmann-La Roche Ltd
24/Statistical Analysis Plan WA29330

The absolute value and change from baseline in DLQI at each visit will be summarized descriptively using observed data. Patients who withdraw or rescue will be summarized for visits up to withdrawal or rescue.

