2.3 DETERMINATION OF SAMPLE SIZE

The primary efficacy endpoint of this study is the proportion of patients (excluding TM patients) achieving a sustained complete remission, as assessed at Week 52, that has been maintained for ≥ 16 consecutive weeks during the 52-week treatment period. With use of limited data available in the literature from randomized clinical trials of MMF and investigator-initiated trials of rituximab ([Beissert et al. 2010](#)), it is estimated that approximately 40% of patients with PV receiving MMF will achieve a sustained complete remission. It is estimated that patients receiving rituximab will induce a sustained complete remission rate of 65%. On the basis of these assumptions, a total of 122 patients randomized to either the rituximab arm or the MMF arm in a 1:1 ratio (61 patients in the rituximab arm and 61 patients in the MMF arm) will yield approximately 80% power in a two-sided test at the 5% significance level. To account for the 10 TM patients excluded from the primary efficacy analysis, approximately 132 patients will be randomized in total. The sample size calculation was performed using nQuery Advisor 7 using the two-group chi-squared test of equal proportions. The primary analysis method using a Cochran-Mantel-Haenszel test adjusting for stratification factors is expected to provide at least 80% power to detect the difference in proportions.

Rituximab—F. Hoffmann-La Roche Ltd
8/Statistical Analysis Plan WA29330

No adjustment will be made for dropouts. Patients withdrawing early from the study or meeting the criteria for treatment failure (including rescue therapy) will be assessed based on available data up until the point of withdrawal or treatment failure only for the primary endpoint. Patients with missing or incomplete data where a status cannot be determined after applying relevant imputation rules will be set to non-responders.

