4.6 VISIT WINDOWS

In general, data for assessments that are collected by scheduled visits will be mapped to visits that appear in the schedule of assessments per the protocol using the actual study day of assessment. Data mapped to scheduled visits will include all data collected up to the reporting cut-off date, and may include withdrawal visits and unscheduled visits.

Data will never be mapped to visits for which the assessment was not scheduled in the protocol (i.e., results for an assessment conducted at an unscheduled visit will be mapped to the appropriate visit at which the assessment was scheduled). Visit windows will be continuous from the midpoint between two consecutive study visits, and will be dependent on the schedule of assessments for each variable independently. An example of the DLQI visit window is given in [Table 1](#). Visit windows for each variable will be constructed in the same manner.

Table 1 Time Windows of Study Days to Assign Study Visit (for DLQI)

Study Visit	Scheduled Study Day (±3 days)	Time Window (Days)
Baseline	1	≤1
Week 12	84	>1 to ≤126
Week 24	168	>126 to ≤224
Week 40	280	>224 to ≤322
Week 52	364	>322 to ≤375

DLQI = dermatology life quality index.

Derived variables such as remission endpoints or assessments that are collected on an ongoing basis, such as flares and oral corticosteroid dose, will be presented using appropriate time intervals.

Data displays that are presented by visit will only include visits at which the assessment was scheduled to be collected. The methods for handling multiple values within a visit window are described in Section 4.10.3.

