4.7 EFFICACY ANALYSIS

The primary and the first five ranked secondary endpoints (listed below) will be tested at an overall 5% significance level using two-sided hypothesis tests. The remaining secondary endpoints will be considered exploratory (Section 2.2.4) and not tested for significance.

To control for overall Type I error, the hypothesis testing on study endpoints will be conducted sequentially starting with the primary endpoint at 5% level of significance. If the null hypothesis relating to the primary endpoint is rejected, the first 5 secondary endpoints will then be tested in a fixed-sequence fashion in the following order:

1. Cumulative oral corticosteroid dose (prednisone or equivalent) over the treatment period
2. Total number of disease flares during the treatment period
3. Time to initial sustained complete remission
4. Time to disease flare
5. Change in health-related quality of life (HRQoL), as measured by the dermatology life quality index (DLQI) score, from baseline to Week 52

If at any step in the testing procedure, the p-value associated with a test is not <0.05, the remaining endpoints below the sequence will not be considered significant.

The mITT population will be the primary population used for the analysis of efficacy outcomes except for duration of sustained complete remission which will be on a subset

Rituximab—F. Hoffmann-La Roche Ltd
16/Statistical Analysis Plan WA29330

of mITT population (see Section 4.7.3.1). Additional analyses will be conducted for sensitivity or exploratory purposes, as described in the relevant sections below.

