1. BACKGROUND

Study WA29330 (PEMPHIX) aims to evaluate the efficacy and safety of rituximab (RTX) versus mycophenolate mofetil (MMF) in patients with pemphigus vulgaris (PV). PV is a rare, serious autoimmune disease characterized by blisters and erosions of the skin and mucosal areas.

Study WA29330 is an international, multicentre, randomized, double-blind, double-dummy, active-comparator, two-arm, parallel-group study, which consists of three periods: a screening period of up to 28 days; a 52-week, double-blinded, treatment period; and a 48-week safety follow up (SFU) period that begins at the time of study treatment completion or discontinuation. All patients who withdraw early from the 52-week treatment period or who complete the 52-week treatment period, must return for post-study treatment SFU assessments at 12, 24, 36, and 48 weeks after either the early withdrawal visit or study treatment completion, respectively.

A separate primary Statistical Analysis Plan (SAP) which describes the statistical methodology and data handling rules used for the 52-week treatment period was finalized before primary database freeze, the analyses completed, and Clinical Study Report (CSR) finalized. This SAP describes the timing and data handling rules to be used for the 48-week SFU period prior to final database lock.

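### The DLQI endpoint is change to Week 52, but the listed model has no treatment-by-visit term and so tests one effect averaged over Weeks 12, 24, 40 and 52

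*SAP*

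**What the plan says.** SAP 4.7 names the fifth and last ranked secondary endpoint as "Change in health-related quality of life (HRQoL), as measured by the dermatology life quality index (DLQI) score, from baseline to Week 52", tested two-sided at 5% if the primary and the four preceding secondary endpoints succeed.

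SAP 4.7.2.5 gives the method: "Change from baseline to Week 52 in DLQI will be analyzed using a maximum likelihood-based repeated measures model". The model adjusts for "treatment arm, region, duration of illness, baseline DLQI score, visit, and an interaction term for visit × baseline DLQI score". The within-patient covariance structure is described only as appropriate. On intercurrent and missing data: "Rescue data will be set to missing, otherwise data will be used in the analysis as observed", with missing scores left to the model. By-visit results are descriptive: "The absolute value and change from baseline in DLQI at each visit will be summarized descriptively using observed data".

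Table 1 in SAP 4.6 and the schedule of assessments put the post-baseline DLQI visits at Weeks 12, 24, 40 and 52. Protocol 6.5.2 defers details of the secondary analyses to the SAP, so nothing there fills the gap.

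**The concern.** In a repeated measures model, the arm difference at a given visit is estimated separately only if treatment is allowed to interact with visit. The listed model has one interaction, and it is with baseline. The fitted arm difference is therefore the same number at all four visits. Requesting an adjusted mean difference at Week 52 from this model returns that common number.

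Two errors can follow if the effect changes over the year. A benefit that builds late is understated and may be missed. A benefit present only early can be declared significant under a Week 52 label.

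**Working it through.** **Inputs from the documents.** Four post-baseline visits (Weeks 12, 24, 40, 52); two-sided 5%; a planned analysis set of "61 patients in the rituximab arm and 61 patients in the MMF arm" (SAP 2.3). The documents state no power, SD, correlation or effect size for DLQI, so there is no DLQI figure to reproduce.

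**Assumptions, for illustration only.**
- SD 6, 7 or 8, the same at every visit; 55 or 61 patients per arm.
- Nine correlation structures: compound symmetry at 0.3, 0.5, 0.7; decay by visit order at 0.5, 0.6, 0.7; decay by the actual 12/16/12-week spacing at 0.5, 0.6, 0.7 per 12 weeks.
- Normal-theory power.

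**Step 1: what the coefficient estimates.** With covariance matrix V of the four visits, the main-effect coefficient weights the visit-specific differences by w = V⁻¹1 / (1′V⁻¹1). With complete data:

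| Structure | Week 52 weight |
|---|---|
| Compound symmetry 0.3–0.7 | 0.25 |
| Decay by visit order 0.5 / 0.6 / 0.7 | 0.333 / 0.357 / 0.385 |
| Decay by actual spacing 0.5 / 0.6 / 0.7 | 0.318 / 0.342 / 0.371 |

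Week 52 thus carries 25–39% of the weight. Monotone missing data lower this: 0.227–0.354 if 10% are missing by Week 52 (4%, 3%, 3% last seen at Weeks 40, 24, 12), and 0.192–0.304 if 25% are missing (10%, 10%, 5%). Setting scores after rescue to missing adds to such loss.

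**Step 2: one case by hand.** SD 7, compound symmetry 0.5, 61 per arm.
- Variance of a patient's four-visit average: 49 × (1 + 3 × 0.5)/4 = 30.6.
- Standard error of the common effect: √(2 × 30.6/61) = 1.00.
- Standard error of the Week 52 contrast: 7 × √(2/61) = 1.27.
- Profile 0/-1/-2/-3: the common effect is -6/4 = -1.5, so z = 1.50 and power is 32%. The Week 52 contrast has z = 3/1.27 = 2.37 and power 66%.
- Profile -3/-2/-1/0: the common effect is again -1.5, so the listed model rejects 32% of the time although the Week 52 difference is zero.
- Constant -3: 85% for the listed model against 66%.

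**Step 3: the full grid, complete data.**

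| True difference at Weeks 12/24/40/52 | Listed model rejects | Week 52 contrast rejects |
|---|---|---|
| 0/-1/-2/-3 | 20–52% | 50–79% |
| -3/-2/-1/0 | 20–52% | 5% |
| -1/-3/-3/-3 | 44–92% | 50–79% |
| -3/-3/-3/-3 | 61–98% | 50–79% |
| 0/0/0/0 | 5% | 5% |

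**Step 4: simulation of the model itself.** 1,000 runs, 61 per arm, SD 7, compound symmetry 0.5, true differences 0/-1/-2/-4. The listed model gave a mean effect of -1.71 (expected -7/4 = -1.75). With treatment × visit added, the Week 52 contrast averaged -3.93 (true -4). Calculated power for this profile is 42% against 88%.

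**Step 5: unequal SDs.** The ranges above hold only if the SD is the same at every visit. With correlation 0.5 and 61 per arm:
- SDs falling 7/6/5.5/5: the Week 52 weight is 0.48. The rising profile is estimated as -2.25, with power 80% against 91%; the reversed profile is rejected 16% of the time.
- SDs rising 5/5.5/6/7: the Week 52 weight is 0.03, and the reversed profile is rejected 80% of the time.

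**The case against.** Four points can be made for the plan.

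- **The term list may be shorthand.** The sentence says the analysis adjusts for treatment arm, which is loose wording, and the sentence before it names Week 52. An omission is possible. But the list spells out one interaction, so it is not merely a list of main effects, and a programmer following it would leave out treatment × visit.
- **A whole-period effect may be intended.** The protocol's DLQI objective names no time point. The SAP, however, words its period-wide endpoints differently: cumulative corticosteroid dose and number of flares refer to the treatment period, while DLQI is tied to Week 52.
- **A constant effect may be reasonable, and the listed model then has more power.** The power point stands. The documents predict no profile, but the design gives little reason to assume constancy. An uninterrupted taper in protocol Table 1 takes 18 weeks from 60 mg (1 + 1 + 8 × 2) or 19 from 80 mg, so patients are still on prednisone at Week 12. The second infusion course starts on Day 168, the scheduled day of the Week 24 visit.
- **The consequences are limited.** DLQI is last in the sequence, nothing depends on it, and the by-visit summaries would show a diverging Week 52 result. This stands, although those summaries supply no model-based or tested Week 52 estimate.

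The numerical ranges also depend on equal SDs across visits. That is a fair restriction on the illustration, but it shows too that an unspecified covariance structure leaves the weights themselves unspecified.

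**Conclusion.** The concern holds. As written, the model neither estimates nor tests the Week 52 difference unless the effect is constant over visits. This follows from the listed terms and needs no outside figure. The test remains valid at 5% for the null of no DLQI difference at any visit.

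The size depends on an effect profile, SD and correlation that the documents do not give. Under the equal-SD assumptions the loss or gain is material in either direction; unequal SDs widen the range further. The primary endpoint and the first four secondary endpoints are unaffected. The point should be fixed, but its reach is one endpoint.

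**What to change.** Add treatment × visit to the model with visit as a categorical factor. Name the Week 52 treatment difference in adjusted mean change, with its 95% confidence interval and p-value, as the quantity tested in the sequence. The average over visits can stay as a supportive result. Separately, it would help to name the covariance structure and a fallback order.

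Before unblinding, this costs one line of SAP text and three model parameters (four visits less one), with no new data. The price is some loss of power if the effect is in fact constant. The 48-week follow-up SAP describes the primary stage as past: "the analyses completed, and Clinical Study Report (CSR) finalized". In that case the Week 52 contrast should be reported as a labelled supplementary analysis, and the common effect should not be described as the Week 52 difference.

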4.7.3 Exploratory Efficacy Endpoints

The following endpoints will provide additional information to assess treatment efficacy during the 52-week double blind treatment period. Exploratory endpoints will be summarized using frequency counts and percentages for categorical data and summary statistics for continuous data. Graphical displays will be used where relevant to show trends over time.

Treatment Failure:

The number and percentage of patients having treatment failure (defined in Section 4.2) from Week 12 to Week 52 will be summarized descriptively.

All data handling methods will follow those used for the derivation and classification of sustained complete remission.

4.7.3.1 Duration of Remission

Throughout this section, remission is referred to as a patient demonstrating the following criteria:

- PDAI^a score = 0
- Prednisone (or equivalent) dose = 0 mg/day

Duration of remission will be calculated as the number of consecutive days a patient is in remission during the 52-week treatment period. Duration of remission will be analyzed using an analysis of covariance (ANCOVA) with logarithmic transformation (or any other suitable transformation depending on the distribution of the data) of duration of remission, adjusting for the stratification factors (duration of illness and geographical region) and presented as days. Patients who demonstrate fluctuating remission flare disease behaviour will be evaluated using their best response (i.e., longest duration) observed during the 52-week treatment period. For patients who withdraw or receive rescue therapy, the duration of remission will be calculated as the number of days in remission up until the point of withdrawal or receipt of rescue, respectively. Patients who never achieved remission will be assigned a duration of 0; this includes withdrawals.

A separate analysis will evaluate the duration of sustained complete remission. This will be conducted on the subset of patients who met the primary endpoint of sustained complete remission, and will follow a similar method to the mITT analysis. The duration of sustained complete remission will begin on the first day that a patient entered remission, providing the response was maintained for at least 16 consecutive weeks. Thus, the minimum duration, in the duration of sustained complete remission analysis, will be 16 weeks.

Rituximab—F. Hoffmann-La Roche Ltd
25/Statistical Analysis Plan WA29330

4.7.3.2 Patient Global Impression of Change

The PGIC is a measure of perceived change in PV symptoms as assessed by the patient. The patient uses a 7-item categorical scale ranging from “very much improved” to “very much worse” to answer “How would you rate the change of your pemphigus vulgaris symptoms since you started taking the study drug?” ([Appendix 7](#)).

The PGIC categories will be summarized by visit up to Week 52. Rescue data will be set to missing from the point of rescue onwards; no imputation will be made for rescue data.

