All patients who withdraw from the treatment period or who complete the total 52-week treatment period must return for post-*Week 52* SFU assessments at 12, 24, 36, and 48 weeks after either the early withdrawal visit or study treatment completion, respectively. Thus, patients will be followed for approximately 1 year in the SFU period. A schedule of assessments during the SFU period is provided in [Appendix 2](#).

Before Week 12, patients who experience treatment failure (as defined in Section [3.1.3](#)) will require an early withdrawal visit and will be followed in the SFU period to receive standard-of-care treatment per the investigator's best medical judgment.

From Week 12 through Week 52, patients who experience treatment failure (as defined in Section [3.1.3](#)) are eligible to receive rescue therapy during the treatment period with another immunosuppressive medication, IV Ig, plasmapheresis, or another treatment or procedure as per the investigator's best medical judgment. An early withdrawal visit is not required for a patient to receive rescue therapy, and patients should continue to be followed in the study per the 52-week treatment period (see [Appendix 1](#)).

If a patient receives rescue therapy with rituximab, the number and timing of infusions will be at the discretion of the investigator. Every effort will be made to maintain the study blind, but the patient may be unblinded at the discretion of the Principal Investigator's safety assessment. Patients who receive rescue infusions with rituximab from Week 12 through Week 24 will not receive the scheduled rituximab or matching placebo infusions on Days 168 and 182. Careful consideration should also be given as to whether MMF/matching placebo are continued following rescue therapy with any immunosuppressive medication.

Evaluation of the primary endpoint will occur at Week 52. To prevent potential unblinding due to observed efficacy or laboratory changes, a dual-assessor approach will be used to evaluate efficacy and safety.

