6.5.2 Secondary Efficacy Endpoints

All secondary efficacy parameters will be listed or summarized and presented in tables or graphs based on the *mITT* population.

The secondary efficacy outcome measures are as follows:

- Cumulative oral corticosteroid dose (prednisone or equivalent) over the treatment period
- Total number of disease flares during the treatment period
- Time to initial sustained complete remission
- Time to disease flare (as defined in Section 3.4.1.2)
- Change in HRQoL, as measured by the DLQI score from baseline to Week 52
- Duration of sustained complete remission
- Patients' impression of change in PV symptoms, as measured by the PGIC score during the treatment period
- Clinician impression of change in patients' PV symptoms, as measured by the CGIC score during the treatment period

Details on the analysis of secondary endpoints will be provided in the SAP.

Given the multiple endpoints, the statistical hypotheses related to the secondary objectives will be tested using a sequential testing procedure to control for the type I error (i.e., probability of a false-positive statistical inference). Full details on methodology to control for the type I error will be provided in the SAP.

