2.2.2 Secondary Efficacy Outcome Measures

The secondary efficacy outcome measures are as follows:

- Cumulative oral corticosteroid dose (prednisone or equivalent) over the treatment period
- Total number of disease flares during the treatment period
- Time to initial sustained complete remission
- Time to disease flare
 - Disease flare is defined as appearance of three or more new lesions a month that do not heal spontaneously within 1 week, or by the extension of established lesions, in a patient who has achieved disease control.
- Change in health-related quality of life (HRQoL), as measured by the dermatology life quality index (DLQI) score, from baseline to Week 52
- Duration of sustained complete remission
- Patients' impression of change in PV symptoms, as measured by the patient global impression of change (PGIC) score, during the treatment period
- Clinician impression of change in patients' PV symptoms, as measured by the clinician global impression of change (CGIC) score, during the treatment period.

The first five secondary efficacy outcome measures will be included in a hierarchical testing procedure to control for Type I error (See Section 4.7); the remaining secondary endpoints will be considered exploratory and will not be tested for Type 1 error.

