4.7.3.3 Clinician Global Impression of Change

The CGIC is a measure of perceived change in PV symptoms as assessed by the clinician. The clinician uses a 7-item categorical scale ranging from “very much improved” to “very much worse” to answer “How would you rate the change in the patient’s pemphigus vulgaris symptoms since the patient started taking the study drug?” ([Appendix 8](#)).

Data for CGIC will be described in the same manner as PGIC, as described in Section [4.7.3.2](#).

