4.7.3.10 Disease Control

The number and percentage of patients in a state of disease control will be summarized by visit up to Week 52. Patients who receive rescue therapy will be considered as not in control from the point of rescue onwards, regardless of the recorded value on the eCRF.

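### PGIC and CGIC ratings are dropped after rescue with no denominator or withdrawal rule, so observed-case percentages at later visits can distort the comparison of arms

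*SAP*

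**What the plan says.** Protocol 6.5.2 lists both global impressions as secondary efficacy outcomes: the patient's "impression of change in PV symptoms, as measured by the PGIC score during the treatment period", and the clinician's "as measured by the CGIC score during the treatment period". SAP 2.2.2 keeps them on the secondary list, but only the first five secondary endpoints enter the testing sequence; "the remaining secondary endpoints will be considered exploratory and will not be tested for Type 1 error".

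The analysis is specified in two short sections. SAP 4.7.3.2: "The PGIC categories will be summarized by visit up to Week 52", followed by "Rescue data will be set to missing from the point of rescue onwards; no imputation will be made for rescue data". SAP 4.7.3.3: "Data for CGIC will be described in the same manner as PGIC".

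Other sections that bear on the point:

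- **Rescue as failure.** SAP 4.2 and Protocol 3.1.3 make the start of any rescue therapy a treatment-failure event.
- **Failure before Week 12.** Under Protocol 3.1.1 these patients "will require an early withdrawal visit and will be followed in the SFU period". SAP 4.5 cuts each patient's data at early withdrawal.
- **Rescue from Week 12.** Protocol 3.1.1 keeps these patients in the treatment-period schedule, so their later ratings are collected.
- **Denominator.** SAP 4.10.1 asks for number and percentage for categorical data and does not say of whom.
- **Disease control.** SAP 4.7.3.10 takes the opposite line on rescue: "Patients who receive rescue therapy will be considered as not in control from the point of rescue onwards".

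**The concern.** A patient who needs rescue has failed by the trial's own definition. Setting that patient's later ratings to missing turns a known poor outcome into no outcome. If the percentages at Weeks 24, 40 and 52 are then taken over patients with a rating, each arm's distribution is conditioned on something that happened after randomisation and that treatment is expected to influence. The arms are no longer compared as randomised.

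The SAP does not treat its other endpoints this way. Disease control counts rescue as not in control. The primary endpoint sets undeterminable status to non-responder (SAP 2.3) and has a tipping-point analysis (SAP 4.7.1.5). DLQI also blanks post-rescue scores, but inside a repeated-measures model (SAP 4.7.2.5). PGIC and CGIC have neither a model nor a failure rule.

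At stake is the readability of two secondary endpoints whose stated objective is to compare rituximab with MMF.

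**Working it through.** **The plan's own figure.** The documents give no figure for PGIC or CGIC. The sample size for the primary endpoint (SAP 2.3: 40% against 65%, 61 per arm, two-sided 5%, about 80% power) supplies the inputs, so I checked it first.

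n per arm = [1.96 × √(2 × 0.525 × 0.475) + 0.8416 × √(0.40 × 0.60 + 0.65 × 0.35)]² / 0.25² = 61.4, rounded up to 62. Power at 61 per arm is 79.7%. The stated figure is reproduced.

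**Illustration: assumptions.**

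- 61 patients per arm (SAP 2.3).
- The planned primary-endpoint rates are borrowed as improvement rates: rituximab 40/61 = 65.6%, MMF 24/61 = 39.3%, a true gap of 26.2 points. The documents give no PGIC or CGIC rates.
- Every patient lost to rescue or withdrawal is a failure, that is, would be rated not improved.
- Percentages use observed patients, so observed rate = improved / (61 − lost).
- The loss counts are mine. The documents give no rescue or withdrawal rate by arm, so a range is shown.

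| Lost, rituximab / MMF | Rituximab | MMF | Gap shown (points) |
|---|---|---|---|
| 0 / 0 | 40/61 = 65.6% | 24/61 = 39.3% | 26.2 |
| 3 / 6 | 40/58 = 69.0% | 24/55 = 43.6% | 25.3 |
| 3 / 12 | 40/58 = 69.0% | 24/49 = 49.0% | 20.0 |
| 6 / 18 | 40/55 = 72.7% | 24/43 = 55.8% | 16.9 |
| 3 / 20 | 40/58 = 69.0% | 24/41 = 58.5% | 10.4 |
| 12 / 12 | 40/49 = 81.6% | 24/49 = 49.0% | 32.7 |
| 12 / 14 | 40/49 = 81.6% | 24/47 = 51.1% | 30.6 |

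With the mITT number as denominator, and lost patients kept in it as not improved, the gap is 26.2 points in every row.

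**Arms truly equal.** Take 30/61 = 49.2% improved in both, with 3 and 12 failures lost: 30/58 = 51.7% against 30/49 = 61.2%. The arm that lost more failures looks better by 9.5 points.

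**When would the arms look the same?** Set 40/(61 − y) = 24/(61 − x), so x = 61 − 24(61 − y)/40. With y = 0, 3 and 6 rituximab losses, x = 24.4, 26.2 and 28.0. There are 61 − 24 = 37 MMF failures, so equality needs 66% to 76% of them to be lost.

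**Who is left out at Week 52.** Rescued patients are left out from rescue onwards, by explicit rule. For withdrawals there is no PGIC or CGIC rule. Both scales are scheduled at the withdrawal visit (Protocol Appendix 1), and SAP 4.6 allows withdrawal-visit data to be mapped by study day. PGIC and CGIC share the DLQI post-baseline weeks, so the DLQI windows in SAP Table 1 should carry over. A withdrawal rating up to Day 126 would fall in the Week 12 window, and one after Day 322 in the Week 52 window. Most earlier withdrawals are therefore absent at Week 52.

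**The case against.** The strongest reply is that the denominator is unstated, not stated to be observed patients. SAP 4.7 names mITT as the primary efficacy population. If the percentages are of mITT, the rescued and withdrawn appear as a shortfall from 100% and nothing is hidden. This stands, and it is why the point is conditional. It also means that one sentence would settle it.

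Three stronger readings are tempting, and the documents do not support them:

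- A reader might infer that the tables cover only patients who did not fail. They do not. Ratings before rescue stay in. Failures on the steroid criteria who receive no rescue and stay in the treatment period keep all their ratings. A late withdrawal rating can enter Week 52.
- A reader might infer that the arms would look alike at Week 52. That needs roughly 24 to 28 of 37 MMF failures lost under the planned rates. Assuming the same improvement rate among those who remain in each arm would produce equality by construction.
- A reader might infer that the arm losing more patients always benefits. It does not on the difference scale: with 12 against 14 failures lost, the gap in favour of rituximab widens from 26.2 to 30.6 points. Patients can also leave for reasons other than failure (Protocol 4.6.1), and some of them may have improved.

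Part of the information is reported elsewhere. SAP 4.3 tabulates discontinuations by arm, treatment failures and rescue. SAP 4.2 promises exploratory summaries that include rescue data for key efficacy assessments, but it does not name PGIC or CGIC. Separate tables do not let a reader rebuild the category distribution.

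**Conclusion.** The point holds in a limited form. The rule that blanks ratings after rescue is explicit; the missing denominator and withdrawal rule are gaps. Together they permit Week 52 tables in which a known class of failures is absent, and absent unequally if the arms differ in rescue.

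In the illustration, moderate imbalance (3 against 12 lost) takes about 6 points off a 26.2-point gap, and heavy imbalance (3 against 20) takes about 16. With equal arms, 3 against 12 lost creates a spurious 9.5-point difference. These figures rest on borrowed improvement rates, assumed loss counts, all lost patients being failures, and an observed-case denominator. Actual size, and sometimes direction, cannot be derived from the documents.

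The consequence is confined to descriptive summaries outside the testing sequence. Type I error, the primary endpoint and the five ranked secondary endpoints are untouched. It is a cheap improvement to how two secondary endpoints are shown.

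**What to change.** In SAP 4.7.3.2 and 4.7.3.3:

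- Use the mITT number in each arm as the denominator at every visit.
- Add two rows below the seven categories: rescued, and withdrawn or missing.
- When an improved proportion is quoted, count rescued patients as not improved, in line with SAP 4.7.3.10. Withdrawn or missing patients stay in the denominator, and their own row shows how much of the shortfall they make up.
- Keep the observed-case table as a supplement.
- Also tabulate the ratings collected after rescue. Counting rescue as not improved is one choice of estimand, and showing the collected ratings lets a reader see the other.

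For disease control, SAP 4.7.3.10 already handles rescue. It only needs to state the mITT denominator and how withdrawals are counted.

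The cost is SAP wording, two table rows and one extra tabulation. No new data are needed. The downside is a slightly longer table.
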